7.6.5 Secondary Efficacy Endpoints Analysis

Analysis of the secondary efficacy endpoints will be based on mITT population and PP population. Descriptive statistics for secondary efficacy endpoints will be presented by treatment group and by study visit where appropriate. All post-baseline data collected will be used in the analyses, including observations occurring after discontinuation of study drug.

7.6.5.1 Change in eGFR, UACR, and sUA from Baseline to Study Weeks 2, 6, 12/ET, and Follow-up Visit

For each of these secondary efficacy endpoints, the ANCOVA model using LOCF described for the primary efficacy endpoint in **Section 7.6.1** will be fitted for the change from Baseline to each specific timepoint, ie, Study Week 2, Week 6, Week 12, and Follow-up Visit.

The MMRM and all observed data (excluding data collected at Follow-up visit) described for the primary efficacy endpoint in **Section 7.6.2** will be fitted for each of these endpoints also.

Note: In the above ANCOVA and MMRM models, Baseline eGFR will be included as a covariate to model change in eGFR from Baseline.

For each of these endpoints, 3 figures will be generated by treatment group: figure to present the mean change from Baseline by visit; figure to present the LS mean change from Baseline to Study Week 12 from the ANCOVA model, and figure to present the LS mean change from Baseline to each post-baseline study weeks from the MMRM.

In addition, the following scatter plots will be generated by treatment group:

- Change in UACR at Study Week 12 from Baseline versus Baseline UACR

- Change in UACR at Study Week 12 versus change in eGFR at Study Week 12 from Baseline
- Change in UACR at Study Week 12 from Baseline versus Baseline eGFR
- Change in UACR at Study Week 12 from Baseline versus Baseline sUA
- Change in UACR at Study Week 12 from Baseline versus Change in sUA at Study Week 12
- Change in UACR at Study Week 12 from Baseline versus Baseline BMI
- Change in UACR at Study Week 12 from Baseline versus Baseline SBP
- Change in UACR at Study Week 12 from Baseline versus Baseline HbA1C
- Change in UACR at Study Week 12 from Baseline versus Baseline 8-OHdG
- Change in UACR at Study Week 12 from Baseline versus Baseline hs-CRP
- Change in UACR at Study Week 12 from Baseline versus Baseline sTNFR1
- Change in eGFR at Study Week 12 from Baseline versus Baseline eGFR
- Change in eGFR at Study Week 12 from Baseline versus Baseline sUA
- Change in sUA at Study Week 12 versus change in eGFR at Study Week 12 from Baseline

7.6.5.2 Proportion of Subjects with >30% Reduction from Baseline to Study Week 12 in UACR

The frequency and percent of subjects with >30% reduction from Baseline to Study Week 12 in UACR will be presented by treatment group. Subjects with missing observations at Study Week 12 are imputed as non-responders for this analysis.

Fisher's exact test will be performed between each TMX-049 group and the placebo group and the exact p-value from each test will be provided. The difference in the percentage of responders between each treatment group and the Placebo group and the exact 95% CLs based on Clopper-Pearson method will also be provided.

Furthermore, the association between having UACR reduction greater than 30% from Baseline to Study Week 12 and the treatment group will be assessed by Logistic regression model. The model will use the incidence of subjects with >30% reduction as the dependent variable, the randomized treatment group, randomization strata of sUA (<6.0 vs \geq 6.0 mg/dL), and UACR (200 to <300 mg/g vs 300 to \leq 3000 mg/g) levels as independent variables, Baseline UACR and Baseline sUA levels as covariates. The estimated odds ratio (and 95% CL) of having >30% reduction versus not having >30% reduction in URCA in any active TMX-049 group versus Placebo group, will be provided.

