7.6 Efficacy and Safety Variables

7.6.1 Efficacy Assessments

7.6.1.1 *Urine Samples for the Calculation of Urinary Albumin-to-Creatinine Ratio*

Two consecutive day mid-stream, first-morning void urine samples will be collected by the subjects at home using the urine collection vessels supplied by the study site at the times indicated in the Schedule of Assessments (Table 2). Subjects will be instructed to return the samples to the study site at their scheduled visit.

The determination of UACR will be performed by [REDACTED].

The results of UACR at Visits 3, 4, 5, 6, and 7 will not be reported to Investigators, subjects, and the Sponsor staff. The Investigators must not measure UACR at local sites.

7.6.1.2 *Blood Samples for the Calculation of Estimated Glomerular Filtration Rate*

Blood samples for the calculation of eGFR will be taken at the times indicated in the Schedule of Assessments (Table 2).

The determination of eGFR will be performed by [REDACTED] using the CKD-EPI formula. The calculation will be based on the serum creatinine measurement in the serum chemistry profile.

7.6.1.3 *Urine Samples for the Analysis of Exploratory Biomarkers*

The mid-stream, first-morning void urine samples collected by the subjects at home using the urine collection vessels supplied by the study site will be used for the analysis of exploratory biomarkers (kidney injury molecule-1 [KIM-1], liver fatty acid-binding protein [L-FABP], 8 hydroxy-2'-deoxyguanosine [8-OHdG]), and N-acetyl- β -D-glucosaminidase (NAG) at the times indicated in the Schedule of Assessments (Table 2). Aliquots of urine will be stored for potential use in other biomarker assays related to the mechanism of action, PK, safety, or renal effects of TMX-049.

The analysis of biomarkers will be performed by [REDACTED].

7.6.1.4 *Blood Samples for the Analysis of Serum Uric Acid*

Blood samples for the analysis of sUA will be taken at the times indicated in the Schedule of Assessments (Table 2).

Serum uric acid will be analyzed as part of the serum chemistry profile performed by [REDACTED] (see Appendix A).

7.6.1.5 *Blood Samples for the Analysis of Exploratory Biomarkers*

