7.10.2 Subject Populations Analyzed

The **All Subjects Population** will consist of any subjects who enrolled in the study (signed informed consent) and had study assessments recorded on the database as per the protocol.

The **Safety Population** will consist of all randomized subjects who received at least one study medication tablet or capsule.

The **Modified Intention-to-Treat (mITT) Population** will be used for the efficacy analysis and will consist of all subjects according to their randomization scheme regardless of whether they experienced protocol deviations. The last post randomization UACR will be carried forward (LOCF) for subjects who did not have a Week 12 UACR determination. Randomized subjects with no post randomization UACR will be excluded from the mITT analysis.

The **Per Protocol Population** will be used as a sensitivity analysis for the primary efficacy endpoint and will consist of all subjects according to their randomization scheme who experienced no major protocol deviations.

The **PK Population** will consist of all subjects who received at least one dose of TMX-049 and have evaluable PK data.

All protocol deviations that occur during the study will be considered prior to database lock for their severity/impact and will be taken into consideration when subjects are assigned to analysis populations. Details of subject assignment to the analysis populations will be listed.

Efficacy will be analyzed using the mITT Population (primary analysis) and the Per Protocol Population (supportive analysis), and safety will be analyzed using the Safety Population. Changes from Baseline will utilize values obtained at Visit 3 (the randomization visit) except for the change from baseline in UACR.

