5.4 Modified Intent-to-treat Population

The mITT population will consist of all randomized subjects who have at least 1 post randomization UACR assessment. Subjects in the mITT population will be analyzed according to their randomized treatment.

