5.5 Per-Protocol Population

The PP population will consist of all subjects in the mITT population who do not experience any important protocol deviations leading to exclusion from the PP population. Subjects in the PP population will be analyzed according to their randomized treatment.

Protocol deviations are defined as any change, divergence, or departure from the study design or procedures defined in the study protocol. Important protocol deviations are a subset of protocol deviations and may significantly impact the correctness, accuracy, and/or reliability of the study data or that may significantly affect a subject's rights, safety, or well-being. **Section 5.5.1** details the deviations.

All protocol deviations that occur during the study will be considered prior to database lock (DBL) for their severity and impact.

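### The eGFR and sUA efficacy models leave out randomised subjects who have post-baseline blood results but no post-randomisation UACR

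*SAP*

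**What the plan says.** SAP 7.6.5 sets the population for the secondary efficacy endpoints, which include change in eGFR and change in sUA: "Analysis of the secondary efficacy endpoints will be based on mITT population and PP population". SAP 7.6.5.1 then fits the ANCOVA with LOCF and the MMRM to both endpoints. SAP Section 5 makes mITT the default for efficacy unless the text specifies otherwise.

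The population definitions are:

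- **SAP 5.4:** "The mITT population will consist of all randomized subjects who have at least 1 post randomization UACR assessment".
- **Protocol 7.10.2:** "Randomized subjects with no post randomization UACR will be excluded from the mITT analysis".
- **SAP 5.5:** "The PP population will consist of all subjects in the mITT population who do not experience any important protocol deviations".

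The specimens differ. For UACR, Protocol 7.6.1 says: "Two consecutive day mid-stream, first-morning void urine samples will be collected by the subjects at home". For eGFR it says: "Blood samples for the calculation of eGFR will be taken at the times indicated". It derives sUA from the serum chemistry sample as well.

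On which observations count, SAP 7.6.5 adds: "All post-baseline data collected will be used in the analyses, including observations occurring after discontinuation of study drug".

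**The concern.** Entry to the eGFR and sUA models depends on a different endpoint, observed after randomisation and on a different specimen. The plan gives no reason for this. A subject whose creatinine and uric acid were measured after baseline, but who never supplied a urine result, contributes nothing to either model.

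Two things are at stake. The smaller is precision, because usable values are not used. The larger is comparability: if the omitted subjects change differently from the rest, or are omitted at different rates by arm, the treatment contrast shifts for a reason unrelated to eGFR or sUA measurement. The effect of each dose on eGFR is the first secondary objective listed, so it deserves the fullest randomised set the data allow.

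**Working it through.** **1. Who is left out.** The definitions combine as follows:

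- eGFR and sUA models: mITT and PP only (SAP 7.6.5).
- mITT: at least one post-randomisation UACR (SAP 5.4; Protocol 7.10.2).
- PP: contained in mITT (SAP 5.5), so it restores nobody.
- Blood results do not depend on home urine (Protocol 7.6.1).

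A subject with blood but no UACR at any post-randomisation visit is therefore in neither model population. SAP 5.2 defines a Randomized population, but SAP 7.6.5 does not use it.

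**2. Where such subjects still appear.** The Safety population needs one dose and no UACR (SAP 5.3). SAP 7.7.2 summarises laboratory values and changes from baseline by arm and visit in that population. Its parameter table lists creatinine, uric acid and eGFR. These summaries carry no inferential comparison (Protocol 7.10.4.4) and group subjects by treatment received.

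**3. The plan's own figures.** Inputs from Protocol 7.10.1 and SAP 2.3: 132 randomised 1:1:1, 10% not in the primary analysis, log-scale difference −0.431, SD 0.670, two-sided 0.05.

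- ln(0.65) = −0.431.
- 132 × 0.9 / 3 = 39.6, about 40 per arm.
- SE = 0.670 × √(2/40) = 0.150, and 0.431 / 0.150 = 2.88. Power is about 82.0% by the normal approximation and 81.1% by the exact noncentral t.

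The stated sample size and power reproduce, and this point does not touch them.

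**4. A ceiling on the number affected.** 132 × 0.10 = 13.2, about 13 subjects; 13.2 / 3 = 4.4, about 4 of 44 per arm. This would be the number only if the planned 10% held, every such subject were an mITT exclusion, and every one had post-baseline blood.

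**5. Size of the effect (assumed inputs).** Let k be the number of blood-without-UACR subjects in an arm of 44. Let D be the difference in mean eGFR change between them and the rest. The documents give neither; k = 0 to 4 and D = 5 to 10 ml/min/1.73m² are assumptions. Taking all 44 to have blood results:

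- Shift in the arm mean = (k/44) × D.
- SE ratio when they are dropped = √(44/(44 − k)).

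| k | Shift, D = 5 | Shift, D = 10 | SE ratio |
|---|---|---|---|
| 0 | 0 | 0 | 1.000 |
| 1 | 0.11 | 0.23 | 1.012 |
| 2 | 0.23 | 0.45 | 1.024 |
| 3 | 0.34 | 0.68 | 1.036 |
| 4 | 0.45 | 0.91 | 1.049 |

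With k = 4, restoring the subjects cuts the SE of the arm mean by 1 − 1/1.049, about 4.7%. If two arms have the same k and D, the shifts cancel in the contrast. If only one arm is affected, the contrast moves by the full tabulated amount. The same formula applies to sUA, with D in mg/dL.

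**The case against.** The strongest reply is that the route to exclusion is narrow. One urine sample is enough for a UACR value (SAP 7.6.1), and a value at any post-randomisation visit admits the subject. Collection supplies for Visit 4 are handed out at Visit 3, reminder calls precede scheduled visits, and withdrawn subjects are asked to attend early termination and end-of-study visits where urine and blood are both scheduled. Many subjects would have both or neither. A single efficacy population with a common denominator is also a defensible choice for secondary endpoints in a Phase 2 trial. All of this stands, and it is why the effect is probably small. It does not explain why an eGFR analysis should require a UACR.

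Four stronger readings are tempting, and the documents do not support them:

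- **The blood results are lost.** They are not. Dosed subjects remain in the Safety-population laboratory summaries and listings. What is missing is any between-group inference that includes them.
- **SAP 7.6.5 contradicts itself.** A reader might set the sentence on using all post-baseline data against the mITT restriction. The two are compatible: one says which subjects are analysed, the other which of their observations count.
- **The omitted subjects are mainly early stoppers, perhaps for renal reasons.** This is a plausible guess, since an unplanned visit is a poor fit with home collection on two mornings, but the documents do not say who would lack a UACR.
- **About 13 subjects will be dropped.** The 10% is not an estimate of blood-without-urine subjects. Protocol 7.1 ties the 40 per arm to completing 12 weeks, whereas under LOCF a non-completer with any post-randomisation UACR stays in mITT.

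**Conclusion.** The point holds as a modest one. The restriction follows directly from the definitions: subjects with post-baseline blood but no UACR are excluded from all between-group eGFR and sUA comparisons, and neither mITT nor PP recovers them. How many there will be is unknown and probably fewer than the planning ceiling of about 4 per arm. Under the assumed ranges, an arm's mean eGFR change shifts by 0 to about 0.9 ml/min/1.73m². The documents give no SD for eGFR change, so this cannot be put in standard-error units without a further assumption. The primary analysis, sample size and power are unaffected. The case for change is that the selection serves no stated purpose and is nearly free to remove.

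**What to change.** In SAP 7.6.5, state: *Change in eGFR and change in sUA will be analysed in all randomised subjects with a baseline and at least one post-baseline value of that endpoint, by randomised treatment.* Keep mITT for the UACR endpoints. Protocol 7.10.2 assigns efficacy to mITT, so record the departure and its reason in SAP Section 8, which now reads as not applicable. Report per arm how many subjects with usable blood results mITT would have dropped, so the effect of the choice can be seen.

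The cost is one sentence, one population flag per endpoint and the Section 8 entry. Denominators will differ slightly between endpoints. Some selection remains, because a subject still needs a post-baseline blood value, but it is no longer selection on a different endpoint.

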3.2 Secondary Efficacy Endpoints

The secondary efficacy endpoints include:

- Proportion of subjects with >30% reduction from Baseline to Study Week 12 (Study Visit 6) in UACR
- Change in eGFR (Baseline compared to Study Weeks 2, 6, 12/ET, and Follow-up visit)
- Change in UACR (Baseline compared to Study Weeks 2, 6, 12/ET, and Follow-up visit)
- Change in renal biomarkers (Baseline compared to Study Weeks 2, 6, 12/ET, and Follow-up visit)
- Change in sUA (Baseline compared to Study Weeks 2, 6, 23/ET, and Follow-up visit)

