7.6 Efficacy

7.6.1 Primary Efficacy Analysis

The primary efficacy endpoint is the change from Baseline to Study Week 12 (Study Visit 6) in log-transformed UACR. The analysis will be based on the mITT population.

The UACR values from Study Visits 2 to 7 are calculated as the mean result from 2 consecutive day mid-stream, first morning void urine samples that are submitted on the morning before and on the day of study visits. If only 1 sample is available, the measurement from that sample is used.

Baseline UACR is defined as the mean of UACR from urine samples collected on Study Visit 3 (Randomization day).

For the primary analysis of the primary efficacy endpoint, the last-observation-carried-forward (LOCF) imputation algorithm will be used, where the last recorded post-baseline value for the same subject is carried forward to the missing Study Week 12 visit.

The change from Baseline to Study Week 12 in log-transformed UACR will be analyzed in an analysis of covariance (ANCOVA) model with randomized treatment, randomization strata of sUA (<6.0 vs \geq 6.0 mg/dL) and UACR (200 to <300 mg/g vs 300 to \leq 3000 mg/g) levels as independent variables. The least square mean (LS mean), p-value, and the corresponding 95% confidence limit (CL) for the change in log-transformed UACR in each treatment group, and the difference of change in log-transformed UACR between each TMX-049 treatment group versus Placebo group will be presented. The adjusted geometric mean of Week 12 to Baseline ratio in UACR with the corresponding 95% CLs for each treatment group, and the ratio of the adjusted geometric mean of Week 12 to Baseline ratio achieved within each treatment group relative to that achieved with Placebo group with 95% CLs will also be provided.

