7.6.2 Secondary Efficacy Analysis

Secondary analysis of the primary efficacy endpoint will use mixed model repeated measures (MMRM) and all observed data. The model will include randomized treatment, randomization strata of sUA (<6.0 vs \geq 6.0 mg/dL) and UACR (200 to <300 mg/g vs 300 to \leq 3000 mg/g) levels, timepoint (Study Week), a treatment-by-timepoint interaction as fixed effects, and subject as a random effect. All post-baseline (excluding data collected at Follow-up visit) observations collected will be used in the MMRM. The MMRM statistics will be based on the restricted maximum likelihood (REML) method for estimation. An unstructured (co)variance structure will be used to model within-subject errors. The Kenward-Roger approximation will be used to approximate the denominator degrees of freedom. The adjusted mean change in log-transformed UACR from Baseline to Study Week 12 for each treatment group and the 95% CLs will be estimated in the framework of the this model, as well as the between-group difference and the 95% CLs for the difference.

Summarization of the inferential statistics will include the LS means, standard error (SE) of the estimates, p-value, and 2-sided CLs. These statistics will be provided for the within treatment group changes from Baseline and for the comparison of TMX-049 versus Placebo for the change from Baseline values. The adjusted

geometric mean of Week 12 to Baseline ratio in UACR with the corresponding 95% CLs for each treatment group, and the ratio of the adjusted geometric mean of Week 12 to Baseline ratio achieved within each treatment group relative to that achieved within Placebo group with 95% CLs will also be provided.

Figures displaying the mean change from Baseline by study week, LS mean change at Week 12 in log-transformed UACR from the ANCOVA model using LOCF, as well as the adjusted geometric mean ratio to Baseline at each study week from MMRM will be presented by treatment group.

Furthermore, the ANCOVA model specified in **Section 7.6.1** will be fitted using observed data in order to check the robustness of LOCF in the primary efficacy analysis.

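### SAP 7.6.5.1 names LOCF for the off-drug Follow-up Visit, although the rule it cites covers only a missing Week 12; if applied there, on-drug serum uric acid values are carried into washout (minor)

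*SAP*

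**What the plan says.** **The Follow-up model.** SAP 7.6.5.1 takes "the ANCOVA model using LOCF described for the primary efficacy endpoint in" Section 7.6.1 and says that, for eGFR, UACR and sUA, it "will be fitted for the change from Baseline to each specific timepoint, ie, Study Week 2, Week 6, Week 12, and Follow-up Visit".

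**The LOCF rule it points to.** In SAP 7.6.1, "the last recorded post-baseline value for the same subject is carried forward to the missing Study Week 12 visit". Protocol 7.10.2 has the same limit, for UACR: "The last post randomization UACR will be carried forward (LOCF) for subjects who did not have a Week 12 UACR determination". Protocol 7.10.4.2 repeats it. No section says what happens to a missing Follow-up value.

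**Other analyses.** The repeated-measures model for these endpoints leaves Follow-up out: "The MMRM and all observed data (excluding data collected at Follow-up visit". SAP 7.6.2 adds an observed-data ANCOVA, but for the primary endpoint: it "will be fitted using observed data in order to check the robustness of LOCF in the primary efficacy analysis". SAP 7.6.5 also states: "All post-baseline data collected will be used in the analyses, including observations occurring after discontinuation of study drug".

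**Status of the endpoint.** SAP 3.2 lists "Change in sUA (Baseline compared to Study Weeks 2, 6, 23/ET, and Follow-up visit" among the secondary endpoints (the 23 is evidently a slip for 12). Visit 7 is 4 weeks after the last dose (Protocol 7.1, SAP 2.2).

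**Windows.** SAP 6.1 assigns values to Follow-up from Day 105. Protocol 7.5.4.6 allows Visit 7 at 28 ± 7 days after Visit 6 or early termination, and Visit 6 is at Day 84 ± 7. SAP 7.7.2 uses nominal visits for laboratory summaries.

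**The concern.** The sentence in SAP 7.6.5.1 attaches LOCF to four timepoints, while the rule it imports was written for one. Two programmers could follow the same text and produce different Follow-up results: one leaves a missing Visit 7 value missing, the other fills it with the last recorded value.

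The choice matters most for sUA, because Follow-up is the visit at which the drug effect should have gone. In the two multiple-dose Phase 1 studies, dosing ended on Day 10 and mean sUA was back at baseline by Day 17 (Protocol 5.4.2) or Day 17/18 (Protocol 5.4.3). Carrying an on-drug value to Visit 7 would make the effect appear to persist after washout.

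Missing Visit 7 samples are foreseen. Protocol 7.5.5 allows telephone contact for subjects who decline to return, and Protocol 7.6.2.1.2 sets an adverse-event reporting limit for subjects without that visit.

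The documents do not clearly supply a second Follow-up test against which the ANCOVA could be checked.

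**Working it through.** **The plan's own figure.** No figure is given for Follow-up. The stated power for the primary endpoint reproduces: ln(0.65) = -0.431, and with SD 0.670 and 40 per group the exact two-sided t-test power is 81.1%, against a stated figure of more than 80%. This point does not affect it.

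**Inputs from the documents.**
- Day 10 mean change in minimum sUA: -61.8% (40 mg), -75.9% (120 mg) and -83.4% (240 mg) (Protocol 5.4.3). The last two bracket the 200 mg arm.
- 132 / 3 = 44 randomized per arm. Tests are two-sided at 0.05 (SAP 7.1).

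**Assumptions.** Mean baseline sUA 5.5-6.5 mg/dL; SD of change 1 mg/dL; full washout by Visit 7; equal share p carried in each arm; no change in carried placebo values; p of 2%, 5% or 10%.

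**Bias if LOCF is applied at Follow-up** = baseline × reduction × p.

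| Share carried | Smallest (5.5 × 0.618 × p) | Largest (6.5 × 0.834 × p) |
|---|---|---|
| 2% | 0.07 mg/dL | 0.11 mg/dL |
| 5% | 0.17 | 0.27 |
| 10% | 0.34 | 0.54 |

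All are false reductions relative to placebo. If LOCF is not applied at Follow-up, the carried-forward bias is 0.

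**Effect on the test.** The variance in an arm is 1 + p(1 - p) × shift². At baseline 5.5 and p = 10%, the shifts are 5.5 × 0.618 = 3.40 and 5.5 × 0.834 = 4.59. The variances are 1 (placebo), 2.04 and 2.89, which pool to 1.98. SE = √(2 × 1.98/44) = 0.300. The bias in SE units is 0.340/0.300 = 1.13 (40 mg) and 0.459/0.300 = 1.53 (240 mg figure). Simulated rejection rates with no true difference, using three-arm pooled variance and the same baseline in both active arms:

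| Share carried | 40 mg | 200 mg bracket |
|---|---|---|
| 2% | about 5% | 6-7% |
| 5% | 8-9% | 11-14% |
| 10% | 16-20% | 28-35% |

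These rates illustrate a ceiling. The reductions are healthy-volunteer nadirs after 10 days, whereas the trial takes one blood sample per visit.

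**UACR.** At the design effect and 10% carried, also assuming full washout, the bias is 0.431 × 0.10 = 0.0431. The ratio is exp(-0.0431) = 0.96. Against an SE of 0.670 × √(2/44) = 0.143, that is 0.3 SE. The documents give no expected eGFR effect, so none is sized.

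**Window.** Visit 6 on Days 77-91 (15 days) and Visit 7 at +21 to +35 (15 offsets) give 225 permitted day pairs. Visit 7 falls by Day 104 only if Visit 6 is on Days 77-83, giving 7 + 6 + 5 + 4 + 3 + 2 + 1 = 28 pairs, all on Days 98-104. This counts calendar combinations and is not a forecast. If both visits cluster at target with an assumed SD of 2-4 days, about 0.4-6% of completers are affected.

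**The case against.** **The literal rule is harmless.** SAP 7.6.5.1 defines no LOCF of its own; it borrows one limited to Week 12, and the protocol agrees. LOCF is also named for Week 2, where no earlier post-baseline visit is scheduled, which looks like an unadapted cross-reference. This stands: the bias arises on one of two readings. A reader might infer that the SAP commits to carrying on-drug values into Follow-up; the cited rule does not support that. The sentence still names LOCF at that visit, so the ambiguity is real.

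**Observed-case data are promised.** SAP 6.2.1 says observed-case datasets will be used for all secondary efficacy endpoints, without imputation, and Protocol 7.10.4.2 mentions an observed-case analysis. This weakens any flat claim that no other Follow-up test exists. However, SAP 6.2.1 introduces that dataset for the repeated-measures model, which excludes Follow-up, and SAP 7.6.2 ties the observed-data ANCOVA to the primary endpoint. Neither clearly provides a Follow-up test.

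**The 10% share is not documented.** A reader might take the 10% non-inclusion in the sample-size section, or the expected 40 completers out of 44, as the Visit 7 missing rate. Neither is. The first concerns the primary endpoint, and the second concerns completing 12 weeks. The objection stands, and low shares belong in the range.

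**The window is a separate matter.** Agreed. A Visit 7 value that falls before Day 105 is not necessarily replaced by an on-drug one. Because all post-baseline data are used, it may itself be the last recorded value.

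**Conclusion.** The point holds as a minor defect in a secondary analysis. LOCF is named at an off-drug visit by reference to a rule that does not reach it. If it is applied there, Follow-up sUA is biased toward false persistence by about 0.07-0.11 mg/dL at 2% carried, rising to 0.34-0.54 at 10%. These figures rest on an assumed baseline and share carried, complete washout, and Phase 1 nadirs used as upper bounds. The error rates also rest on an assumed SD. At 2% the error rate is close to nominal.

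The documents do not support a wider conclusion. The primary Week 12 analysis is unaffected, the UACR effect is small, and the sUA objective concerns the 12-week treatment period (SAP 2.1). Observed by-visit descriptive summaries are also planned and could expose a discrepancy. The Day 105 window start is a second, independent flaw: it keeps some permitted Visit 7 samples out of Follow-up under either reading.

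**What to change.** State in SAP 7.6.5.1 that LOCF is not used at the Follow-up Visit, and that the Follow-up ANCOVA uses observed Visit 7 values assigned by nominal visit, as SAP 7.7.2 already does for laboratory data. Note this exception in SAP 6.1, which otherwise prescribes day windows for by-visit secondary analyses. Leave the LOCF handling and windows for the on-treatment visits as written.

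The cost is slightly fewer subjects at Follow-up: at 10% missing, 44 × 0.9 = 39.6, about 40 per arm. Precision need not suffer. Under the assumptions above, observed-only analysis gave an SE of about 0.23, against 0.30-0.33 with LOCF, and an error rate of about 5%. That presumes that subjects missing Visit 7 resemble those seen.

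One side effect should be recorded. An early terminator's Visit 7 value can fall in the existing Week 12 window (termination on Day 50 puts Visit 7 at Day 78), so it could count at both Week 12 and Follow-up. This change leaves that as it is.
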